## STUDY PROTOCOL

### Objective

To assess the influence of physical therapy on diaphragm muscle, via manual release or active mobilization, in subjects with rotator cuff injury comparing with a standard treatment of shoulder myofascial trigger points release

### Methods

#### Randomisation

Patients who meet the eligibility criteria are randomised to receive any of three different treatments through the informatic application provided by the web [www.randomization.com](http://www.randomization.com).

#### Interventions

This study is a randomised controlled trial, the protocol intervention includes:

- 1.- Preintervention assessment of shoulder mobility: flexion, abduction and external rotation at 90° abduction in supine, registered with a Baseline digital inclinometer.
- 2.- Preintervention Numerical Rating Pain Scale in shoulder mobility: flexion, abduction and external rotation at 90° abduction standing.

3.- Preintervention Pain pressure threshold assessment with an algometer in supraespinatus tendon and xiphoid process.

4.- Intervention treatment in each arm:

a.- Experimental group 1: 3 diaphragm stretching techniques according to Chaitow, Ward and Ricard, performed by a physical therapist are employed in this experimental group during 10 minutes. The participants are situated in a seated, supine and side bending position.

b.- Experimental group 2: diaphragm mobilization through active hipopressive gymnastic exercise according to Caufriez in two different postures.

c.- Active comparator group: A ischemic compression technique in most painful myofascial trigger points in the infraespinatus and supraespinatus muscle during one minute each one.

5.- Postintervention assessment of shoulder mobility: flexion, abduction and external rotation at 90° abduction in supine, registered with a Baseline digital inclinometer.

6.- Postintervention Numerical Rating Pain Scale in shoulder mobility: flexion, abduction and external rotation at 90° abduction standing.

7.- Postintervention Pain pressure threshold assessment with an algometer in supraespinatus tendon and xiphoid process.

8.- Statistical analysis and results interpretation.

Every assessment and treatment is performed by a physical therapist who has more tan 10 years of experience in that kind of interventions.

Effects of Diaphragm Muscle Therapy on Pain and Shoulder Movement in Subjects With Rotator Cuff Injuries

Unique Protocol ID: UComplutenseMadrid Fasisifer1

Official Title: Effects of Diaphragm Muscle Therapy on Pain and Shoulder Movement in Subjects With Rotator Cuff Injuries

Investigator: [name]

Sponsor: Universidad Complutense de Madrid

Identifiers: NCT ID not yet assigned

Secondary IDs: 2017-003316-39 [EudraCT Number]

Date: September 24th, 2017

STATISTICAL ANALYSIS PLAN

Unique Protocol ID: UComplutenseMadrid Fasisifer1

Official Title: Effects of Diaphragm Muscle Therapy on Pain and Shoulder Movement in Subjects With Rotator Cuff Injuries

Investigator: [name]

Date: September 24th, 2017

STATISTICAL ANALYSIS PLAN

First, a global descriptive analysis will be conducted in all of the three clinical trial arms considering every assessable individual. Second, the homogeneity between the three groups will be analyzed, proceeding a n/2 homogeneity preanalysis. Finally, an analysis will be conducted comparing the resulting variables of all of three groups, it is expected a descriptive study using the software package SPSS statistics. The results will be evaluated with the description of the mean, standard deviation and quartiles if a normal distribution is present; attaching the median value and interquartile range if an asymmetric distribution is present. The qualitative variables will be assessed in frequency and percentage. In the analytical phase, the valid statistical tests will be used according to the comparing variable (Chi square, t-student, ANOVA or their non parametric variants if applicable. In order to estimate the magnitude of the effect, the risk relative reduction, the risk absolute reduction and the sample size needed will be calculated.

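### The SAP leaves open whether post-treatment values or changes are compared between arms and uses no pre-treatment covariate; a prespecified ANCOVA would close that choice and, for roughly normal data, usually gain precision

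*SAP*

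**What the plan says.** The Protocol, under Interventions, lists three groups of measurements before treatment (steps 1-3) and repeats them after it (steps 5-7). Range of motion is taken in three movements: "Preintervention assessment of shoulder mobility: flexion, abduction and external rotation at 90° abduction in supine", and later "Postintervention assessment of shoulder mobility: flexion, abduction and external rotation at 90° abduction in supine". Pain is rated in the same three movements ("Preintervention Numerical Rating Pain Scale in shoulder mobility: flexion, abduction and external rotation at 90° abduction standing", repeated at step 6). Pressure pain threshold is taken at two sites at steps 3 and 7. That makes 3 + 3 + 2 = 8 numeric outcomes, each with a pre and a post reading. The Objective frames the two diaphragm treatments as "comparing with a standard treatment of shoulder myofascial trigger points release".

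The SAP is one paragraph. On the between-arm analysis it says "an analysis will be conducted comparing the resulting variables of all of three groups". On tests it says "the valid statistical tests will be used according to the comparing variable (Chi square, t-student, ANOVA or their non parametric variants if applicable". Before that comes a baseline step: "the homogeneity between the three groups will be analyzed, proceeding a n/2 homogeneity preanalysis". For effect size it says "the risk relative reduction, the risk absolute reduction and the sample size needed will be calculated".

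It does not define the compared variables as post values, changes or percentage changes. It names no ANCOVA, regression or covariate, and attaches no consequence to the homogeneity step.

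**The concern.** With a pre and a post reading on every outcome, a t-test or ANOVA can be run on post values or on changes. These are different tests with different standard errors, and which is stronger depends on the pre-post correlation r, which the documents do not give. An analyst following the SAP could run either, and nothing in the text stops the choice from being made after both results are known.

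The pre-treatment reading is already collected and is often the strongest predictor of the post reading, yet no listed test uses it as a covariate. The only effect measures named are risk reductions. For degrees, pain ratings and pressure thresholds these need a cut-off, and the SAP gives none, so no stated effect measure fits the numeric outcomes as recorded.

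**Working it through.** **Inputs.** From the documents: eight pre/post outcomes, three randomised arms, and the list of tests. The documents state no arm size, alpha, power, SD, effect size or r, so there is no planned figure to reproduce. Assumed here: two-sided 5%, equal pre and post SDs, normal data, a 0.6 SD difference, 10 to 30 per arm, r from 0 to 0.9.

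**Precision.** The large-sample variance of a between-arm difference, relative to a comparison of post values (= 1), is 2(1 - r) for changes and 1 - r² for ANCOVA. ANCOVA is never larger than either:
- against post values, 1 - (1 - r²) = r² ≥ 0;
- against changes, 2(1 - r) - (1 - r²) = (1 - r)² ≥ 0.

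So the gain vanishes at r = 0 (against post values) and at r = 1 (against changes).

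**Power.** Simulated with three arms of 20, pooled error and one pairwise contrast (40,000 trials per setting):

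| r | Variance: post / change / ANCOVA | Power: post / change / ANCOVA |
|---|---|---|
| 0 | 1 / 2.0 / 1.00 | 46 / 26 / 46% |
| 0.3 | 1 / 1.4 / 0.91 | 46 / 35 / 49% |
| 0.5 | 1 / 1.0 / 0.75 | 46 / 47 / 57% |
| 0.7 | 1 / 0.6 / 0.51 | 46 / 67 / 73% |
| 0.8 | 1 / 0.4 / 0.36 | 46 / 84 / 87% |
| 0.9 | 1 / 0.2 / 0.19 | 46 / 99 / 99% |

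At r = 0 the unrounded figures are 46.2% for post values and 45.5% for ANCOVA, a loss of 0.7 point. At r = 0.7 the three powers are 26/39/43% with 10 per arm and 63/84/89% with 30.

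Hand check at r = 0.7, 20 per arm. The standard error on post values is √(2/20) = 0.316 SD; on changes 0.316 × √0.6 = 0.245; with ANCOVA 0.316 × √0.51 = 0.226. The ratios 0.6/SE are 1.90, 2.45 and 2.66. Subtracting 1.96 gives normal-approximation power of about 48%, 69% and 76%, slightly above the simulated 46%, 67% and 73%, as expected before small-sample corrections.

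**Repeated measures.** If ANOVA is read as repeated measures with two time points, its group-by-time test is the change-score ANOVA: on one simulated data set of three arms of 20, both gave F = 8.913. It does not use the pre value as a covariate.

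**Does ANCOVA settle the choice?** Fitted to post values and then to changes on the same data, it gave identical arm coefficients (-0.094, 0.055, 0.296). Only the baseline slope moved, from 0.437 to -0.563, a shift of exactly 1. The arm comparison is the same either way.

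**Type I error.** With any one test fixed in advance it is about 5%. If either of post or change may be reported, simulation gives 8.2-9.6% per contrast over r = 0 to 0.9 and 10 to 30 per arm (9.5% at r = 0.7, 20 per arm). This is plausible: the two estimates correlate at √((1 - r)/2), which falls from 0.71 at r = 0 to 0.22 at r = 0.9, and two independent 5% tests would give 1 - 0.95² = 9.75%.

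**Skewed or bounded data.** Two arms of 20, assumed r near 0.7; Mann-Whitney on changes against ANCOVA: 81 against 74% with exponential errors, 77 against 71% with exponential margins, and 52 against 66% for a rounded 0-10 pain rating. The order depends on the data model.

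**The case against.** The strongest reply is that nothing here is invalid. Randomisation makes a comparison of post values or of changes fair on average, and prespecifying either would close the choice without ANCOVA. Against changes the gain is modest: 6 points at r = 0.7, 3 at r = 0.8 and almost none at r = 0.9. The SAP foresees asymmetric distributions, where a rank test on changes can match or beat ANCOVA. All of this stands. What remains is that the SAP prespecifies neither quantity, and that r, which decides between them, is unknown.

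Four stronger readings are tempting, and the documents do not support them:

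- **That the planned tests are biased, or that the sponsor will pick the better result.** The SAP says nothing of the kind; it is silent on which quantity is tested.
- **That 8-10% is a ceiling.** It is the figure for one choice. The SAP also leaves open percentage change and the non-parametric variants. With two arms of 20, r = 0.7, and assumed means of 100 before and 110 after with SD 15, adding percentage change gives about 11%, and adding rank tests as well about 12%.
- **That the homogeneity step would catch, or would miss, an imbalance of a given size.** The SAP names no test or level and does not explain n/2, so no detection limit can be calculated.
- **That a repeated-measures ANOVA as a whole equals a change-score analysis.** Only its group-by-time test does; the group main effect tests the pre/post average.

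**Conclusion.** The point holds as one of precision and an open analytical choice, and the SAP should be amended. For roughly normal data with equal pre and post SDs, ANCOVA was above the better of the two alternatives, or within 1 point of it, at every r examined. At 20 per arm and 0.6 SD, the penalty for the wrong unadjusted choice is larger than the gain of ANCOVA over the right one. At r = 0.3, changes lose 46 - 35 = 11 points to post values; at r = 0.7, post values lose 67 - 46 = 21 points to changes. ANCOVA avoids having to guess r.

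These sizes rest on assumed r, arm size and effect size. For skewed data the case for ANCOVA is the fixed choice and an interpretable adjusted difference, not power.

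**What to change.** Add to the SAP:

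> Each post-intervention numeric outcome will be analysed by ANCOVA with treatment arm (three levels) as factor and that outcome's own pre-intervention value as covariate, whatever the homogeneity check shows. The ANCOVA p-value and 95% CI are the primary result.

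Report the adjusted mean difference with 95% CI for each diaphragm arm against the trigger-point comparator, which is the comparison in the Protocol's Objective. For these outcomes it takes the place of the relative and absolute risk reductions.

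Name any rank or permutation test in advance as a sensitivity analysis that is always reported and never replaces the primary result. A rule that switches tests when residuals look skewed would reopen the choice.

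The cost is SAP wording and one degree of freedom per model; both readings are already collected. Two contrasts on eight outcomes make 2 × 8 = 16 comparisons. This change does not deal with that multiplicity, which needs its own statement.

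### Eight outcomes in three arms are to be tested with no primary outcome, multiplicity rule or formal contrast, so the plan does not say which result decides the objective

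*SAP*

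**What the plan says.** The Protocol's Objective is comparative: diaphragm treatment, "via manual release or active mobilization", is assessed by "comparing with a standard treatment of shoulder myofascial trigger points release". Patients are randomised to three arms (Methods, Randomisation): manual diaphragm techniques (experimental 1), active diaphragm exercise (experimental 2) and trigger point compression (comparator).

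The Interventions section takes the same eight measures before and after treatment:

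- Steps 1 and 5, three angles: "Preintervention assessment of shoulder mobility: flexion, abduction and external rotation at 90° abduction in supine" and "Postintervention assessment of shoulder mobility: flexion, abduction and external rotation at 90° abduction in supine".
- Steps 2 and 6, three pain scores: "Preintervention Numerical Rating Pain Scale in shoulder mobility: flexion, abduction and external rotation at 90° abduction standing" and "Postintervention Numerical Rating Pain Scale in shoulder mobility: flexion, abduction and external rotation at 90° abduction standing".
- Steps 3 and 7, two pressure thresholds: "Preintervention Pain pressure threshold assessment with an algometer in supraespinatus tendon and xiphoid process", repeated after treatment.

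The SAP compares the outcome variables across all three groups. It describes the work as a descriptive study, then sets out an analytical phase in which "the valid statistical tests will be used according to the comparing variable (Chi square, t-student, ANOVA or their non parametric variants if applicable". Effect size is to be expressed as relative and absolute risk reduction. Neither document states a significance level, a primary outcome, an order of testing, a multiplicity rule, or which pairs of arms the t-test is for.

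**The concern.** The objective asks one question, and the plan offers many tests that could answer it without ranking them. Three choices are left open:

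- which of the eight outcomes counts;
- which comparison counts: a three-group test, each diaphragm arm against the comparator, or both diaphragm arms pooled against it;
- which form of the outcome is compared: post value, change, or post value adjusted for baseline.

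Each open choice raises the chance of a nominally significant result when the treatments are equal. A claim that diaphragm therapy differs from standard treatment could then rest on whichever outcome gave the smallest p-value, and a reader could not tell from the plan whether that outcome was the intended one. The plan also makes no stated use of the eight baseline values it collects.

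**Working it through.** The plan states no error rate, sample size or power, so there is no figure of its own to reproduce.

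**Inputs from the documents.** Three arms. Outcomes: 3 angles + 3 pain scores + 2 thresholds = 8. Pairs of arms: 3 per outcome, 8 × 3 = 24 in all. Pairs involving the comparator: 2 per outcome, 8 × 2 = 16.

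**Assumed inputs.** Two-sided 5% per test, normal outcomes, 20 per arm, and correlation between outcomes from 0 to 0.9. A block case uses 0.7 within a measurement type and 0.3 between types.

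**Step 1, independent outcomes.** With one ANOVA per outcome, P(at least one p<0.05) = 1 − 0.95^8 = 1 − 0.663 = 33.7%.

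**Step 2, correlated outcomes.** Three equal arms were simulated with eight correlated outcomes. For each outcome, F = n × (variance of the arm means) / (mean of the arm variances) was compared with the 95% point of F on 2 and 3n − 3 degrees of freedom. Two-sample t-tests with no ANOVA gate were run on the same data. Chance of at least one p<0.05 at 20 per arm:

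| Correlation | 8 ANOVAs | 16 comparator pairs | All 24 pairs |
|---|---|---|---|
| 0 | 34% | 53% | 65% |
| 0.3 | 30% | 49% | 60% |
| 0.5 | 26% | 42% | 51% |
| 0.7 | 20% | 33% | 41% |
| 0.9 | 12% | 21% | 27% |
| Block | 26% | 42–43% | 52–53% |

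Sample size hardly matters for the ANOVA column. From 5 to 30 per arm, the figure goes from 26.8% to 25.5% at correlation 0.5 and from 13.1% to 12.3% at 0.9.

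**Step 3, form of the outcome.** For a single outcome, taking the smallest p-value among post value, change and ANCOVA gives 9.5%, 9.8% and 10.1% at pre-post correlation 0.3, 0.5 and 0.7. Each form alone stays at 4.9% to 5.2%.

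**Step 4, what a three-group ANOVA tells us.** Write the true means as m0 (comparator), m1 and m2. If m1 = m0 and m2 = m0, all three are equal. A correct rejection therefore means that at least one diaphragm arm differs from the comparator, but it does not say which. The table gives the share of significant ANOVAs in which neither comparator contrast passes Dunnett:

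| True means m0/m1/m2 (SD units) | 10 per arm | 20 per arm | 40 per arm |
|---|---|---|---|
| 0/0.8/0.8 | 1.4% | 0.5% | 0.1% |
| 0/0.8/0 | 27% | 17% | 5.5% |
| 0/+0.4/−0.4 | 47% | 47% | 32% |

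The follow-up test therefore seldom fails to identify an arm when both diaphragm arms differ from the comparator by the same amount in the same direction. It fails more often otherwise.

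**Step 5, one primary outcome and two comparator contrasts.** At 20 per arm, the chance of any false positive is 9.0% unadjusted and 5.0% with Dunnett. Critical values on 3 × 20 − 3 = 57 degrees of freedom are 2.002 (unadjusted), 2.268 (Dunnett) and 2.302 (Holm first step). An effect with 80.0% power at 2.002 has noncentrality 2.85, since 0.90 SD × √(20/2) = 2.85. The noncentral t then gives 71.9% at 2.268 and 70.7% at 2.302. For the same effect, ANCOVA with Dunnett has 71.4%, 76.3%, 83.8% and 95.3% power at pre-post correlation 0, 0.3, 0.5 and 0.7.

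**The case against.** **The SAP calls the work descriptive.** It does, and a descriptive trial needs no multiplicity control. But the same paragraph plans an analytical phase with hypothesis tests, and the Objective is a comparison. The phrase softens the point without removing it. A clear statement that the trial is descriptive throughout would be a legitimate answer.

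**The comparison is named.** The Objective does identify trigger point release as the comparator. What is missing is the formal contrast: each diaphragm arm, or both pooled.

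**The numbers rest on inputs the plan does not give.** This stands as a limit on precision. A reader might infer that 26% is this trial's false-positive rate. The documents do not support that, because it is one assumed correlation under one reading of an open list of tests. Across the assumed correlations, however, even the lowest ANOVA figure is more than twice 5%.

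**Stronger readings to avoid.** A reader might infer that a significant three-group ANOVA can be true while neither diaphragm arm differs from the comparator. Step 4 of the working shows that it cannot. Type I error aside, the difficulty is only in identifying the arm. A reader might also infer that the error rate exceeds the ANOVA range only if all 24 pairs are tested. That is wrong too: the 16 comparator pairs, which are closest to the Objective, already exceed it at each correlation.

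**ANCOVA, Dunnett and Holm are choices among valid methods.** Agreed. What has to be settled is that a choice is stated in advance. ANCOVA is suggested because the baselines are already collected.

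**Conclusion.** The concern holds, and it should be settled before outcome data are seen. In the text supplied, nothing determines which outcome, contrast or form of the variable answers the Objective. The size is best given as a range that depends on how the open test list is read: about 12% to 34% with one ANOVA per outcome, 21% to 53% with the two comparator pairs, and 27% to 65% with all three pairs. These figures assume 5% per test, normal outcomes, equal treatments and correlations from 0.9 to 0. Choosing the form of the outcome after seeing the data adds a separate inflation, from 5% to about 10% for a single outcome.

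The documents do not show that any outcome will be picked by its p-value. The finding is that the plan as written would not prevent it.

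**What to change.** Amend the SAP before outcome data are seen:

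1. Name one primary outcome from the eight already collected. The choice is the sponsor's.
2. Estimate experimental 1 versus comparator and experimental 2 versus comparator from one ANCOVA of the post-intervention value, adjusted for the pre-intervention value of that outcome. Name a rank-based fallback and state when it applies.
3. State whether the two contrasts are controlled together at two-sided 5% (Dunnett, or Holm, which also works with rank tests) or are separate questions at 5% each, accepting about a 9% chance of any false positive.
4. Report the other seven outcomes, and experimental 1 versus 2, as secondary: estimates with 95% confidence intervals and no confirmatory claim.
5. Give the ANCOVA mean differences as the effect sizes for the continuous outcomes. Keep risk reductions only for outcomes with a responder cut-off defined in advance.
6. If the whole trial is meant to be descriptive, say instead that no p-value will support a confirmatory claim.

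**Cost.** No new data are needed, because the baselines are already measured. The change is to SAP wording, provided outcome data are still unseen; the documents do not give the trial's status. Seven outcomes lose any confirmatory standing. With joint control at an assumed 20 per arm, 80% power falls to about 72% (Dunnett) or 71% (Holm first step). Baseline adjustment recovers none of this at pre-post correlation 0, part of it at 0.3, and all of it by about 0.5. Declaring separate questions avoids the power loss, at the 9% error rate in item 3.

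### The SAP measures the size of effect by risk reductions, but every outcome is a measurement or score with no event defined, and no between-arm difference with a confidence interval is planned

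*SAP*

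**What the plan says.** The SAP is a single paragraph. It plans summaries by arm: mean, SD and quartiles, or median and interquartile range when the distribution is asymmetric. For categorical data, "The qualitative variables will be assessed in frequency and percentage". On testing, "In the analytical phase, the valid statistical tests will be used according to the comparing variable", with chi-square, t-test, ANOVA or non-parametric equivalents listed. Its last sentence is the only one on size of effect: "the risk relative reduction, the risk absolute reduction and the sample size needed will be calculated".

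The protocol's Interventions section lists what is assessed before and after treatment. The post-treatment items are:

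- step 5: "Postintervention assessment of shoulder mobility: flexion, abduction and external rotation at 90° abduction in supine, registered with a Baseline digital inclinometer"
- step 6: "Postintervention Numerical Rating Pain Scale in shoulder mobility", for the same three movements
- step 7: "Postintervention Pain pressure threshold assessment with an algometer in supraespinatus tendon and xiphoid process"

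The Objective sets the contrast: diaphragm therapy, manual or active, "comparing with a standard treatment of shoulder myofascial trigger points release".

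**The concern.** A relative or absolute risk reduction compares the proportion of patients with an event in two arms. A range of motion in degrees, a pain score or an algometer reading has no such proportion until someone chooses a cut-off, and the plan chooses none. It also does not say which outcome, or which two of three arms, the risks would be taken from.

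The third item, a required sample size, is ambiguous. If it is meant as the number needed to treat, it has the same fault. Read literally, it can be computed without a cut-off but does not measure an effect.

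The trial exists to say how diaphragm therapy compares with trigger-point treatment. The plan does not say how the size of that difference, with its uncertainty, will be estimated. If a cut-off is supplied later, it will influence the reported result and could be chosen after the data are seen.

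**Working it through.** **Step 1: match each outcome to the planned measure.**

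| Outcome (Interventions) | Number | Type | Event or cut-off defined? |
|---|---|---|---|
| Shoulder mobility, inclinometer | 3 movements | measured | no |
| Pain rating on movement | 3 movements | scored | no |
| Pressure pain threshold, algometer | 2 sites | measured | no |

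That makes 3 + 3 + 2 = 8 quantities, none of them yes/no. The word threshold in the last row names the quantity measured and is not a cut-off for an event. The SAP mentions qualitative variables and chi-square in general terms, but neither document names a qualitative outcome. Neither document mentions a between-arm difference, a confidence interval or a named pair of arms. This settles the point without arithmetic.

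**Step 2: how much would the missing cut-off matter?** The documents give no sample size, SD, expected effect or event rate, so there is no figure of the plan's to reproduce and every input below is an assumption. Let improvement in a score be normal with SD 2, with mean m0 in the comparator and m0 + 1 in a diaphragm arm. Let the bad event be an improvement of less than c points. Then

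- p0 = Φ((c − m0)/2), p1 = Φ((c − m0 − 1)/2)
- RRR = 1 − p1/p0, ARR = p0 − p1, NNT = 1/ARR

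With m0 = 1:

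| c | p0 | p1 | RRR | ARR (points) | NNT |
|---|---|---|---|---|---|
| 0.5 | 0.401 | 0.227 | 43.5% | 17.5 | 5.7 |
| 1 | 0.500 | 0.309 | 38.3% | 19.1 | 5.2 |
| 2 | 0.691 | 0.500 | 27.7% | 19.1 | 5.2 |
| 3 | 0.841 | 0.691 | 17.8% | 15.0 | 6.7 |
| 4 | 0.933 | 0.841 | 9.8% | 9.2 | 10.9 |

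Over the same cut-offs, RRR runs from 33.0% to 4.5% with means 0 and 1, and from 53.4% to 17.8% with means 2 and 3. With means 1 and 2, SD from 1.5 to 2.5 and c from 1 to 4, RRR lies between 7.0% and 49.5% and ARR between 6.8 and 24.8 points.

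**Step 3: the alternative on the same assumptions.** The mean difference is 1 point whatever the cut-off. The half-width of its unadjusted 95% confidence interval is t(0.975, 2n − 2) × 2 × √(2/n): 1.28 points at 20 per arm and 1.03 at 30 per arm (arm sizes also assumed).

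Dichotomising also loses information. At two-sided 5% and 80% power, the mean difference needs 63 per arm at SD 2. The responder comparison needs 102 per arm at c = 1 or 2, 124 at c = 3 and 185 at c = 4.

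**Step 4: a conditional risk.** Suppose the cut-off were picked from the data as the best of 1, 2, 3 or 4 points and then tested. A simulation used 20,000 runs, two arms with no true difference, and integer-rounded improvements with mean 2 and SD 2.

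| Test at p < 0.05 | Best of four, n = 20 | Best of four, n = 30 | Fixed cut-off |
|---|---|---|---|
| Chi-square, uncorrected | 14.6% | 14.4% | 4.7–4.9% |
| Chi-square, Yates | 6.1% | 7.6% | 1.8–2.6% |
| Fisher | 7.3% | 7.6% | 2.2–2.6% |

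The plan does not say this will be done.

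**The case against.** The best defence is that little is lost. Arm means and SDs will be reported, and t-tests or ANOVA compare the arms. A reader given means, SDs and group sizes can work out an unadjusted difference and its interval. That is correct, and it limits the harm: the randomised comparison survives and no bias is shown. But a test is not a planned estimate, and the SAP commits to no difference, interval or pair of arms. If the data are asymmetric, the planned medians and interquartile ranges do not directly give an interval for the difference.

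A second defence is that the risk measures are meant only for qualitative variables. The sentence carries no such condition, and no qualitative outcome is named.

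The illustration has limits, and these objections stand:

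- For cut-offs from 1 to 3 points, ARR moves only from 19.1 to 15.0 points and NNT from 5.2 to 6.7. The sensitivity is chiefly in RRR.
- If pain is scored in whole numbers, which the documents do not say, cut-offs of 0.5 and 1 define the same event.
- The SAP says the risk measures will be calculated, not tested, so the error rates in Step 4 describe a possible misuse and carry no weight in the conclusion.

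**Conclusion.** The concern holds. The mismatch between risk measures and measured outcomes follows from the two documents alone and rests on no assumption. The plan's only two unambiguous measures of effect cannot be computed as written, and no usable one is named in their place. This is an error in the stated analysis and not just missing detail, so it should be corrected before any data are analysed.

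The size rests wholly on assumed values. For one fixed 1-point difference at SD 2 with means 1 and 2, RRR could be reported as anything from 43.5% to 9.8%, and NNT as anything from 5.2 to 10.9, depending on a cut-off the plan does not give. The arm summaries and hypothesis tests are not affected.

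**What to change.** Replace the closing sentence of the SAP with wording such as:

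> For each outcome, the magnitude of effect will be the difference in means between each diaphragm arm and the active comparator, in the units measured, with a 95% confidence interval, adjusted for the baseline value. If the distribution is asymmetric, the difference in medians with a 95% confidence interval will be reported.

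Name the interval method for medians (a bootstrap interval, for example). Delete the relative and absolute risk reductions and the required sample size. Alternatively, keep risk measures as a secondary responder analysis, with the outcome, threshold and pair of arms fixed before data are seen.

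Baseline adjustment uses values already collected (for pain, "Preintervention Numerical Rating Pain Scale in shoulder mobility"). Its gain in precision depends on a baseline–outcome correlation the documents do not give, and it is not needed to cure the mismatch.

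Eight outcomes and two contrasts give 16 intervals. The SAP should say how these are to be read together, and whether the two diaphragm arms will also be compared with each other.

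The cost of the core change is one sentence of SAP wording, with no extra patients or measurements.

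### The SAP's effect measures (two risk reductions and a needed sample size) do not fit outcomes that are all measurements or scores with no yes/no event defined

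*SAP*

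**What the plan says.** The SAP is a single paragraph. After the descriptive steps it turns to testing: "In the analytical phase, the valid statistical tests will be used according to the comparing variable", with the list "Chi square, t-student, ANOVA or their non parametric variants if applicable". The next and last sentence gives the effect measures: "In order to estimate the magnitude of the effect, the risk relative reduction, the risk absolute reduction and the sample size needed will be calculated". The third of these ("the sample size needed will be calculated") is not defined. The text reviewed contains no other effect measure. It gives no between-arm difference, no confidence interval, and no alpha or power.

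Under Randomisation, the Protocol has patients "randomised to receive any of three different treatments". Under Interventions it lists the outcomes, measured before and after treatment:

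- mobility in three movements by inclinometer ("Postintervention assessment of shoulder mobility: flexion, abduction and external rotation at 90° abduction in supine, registered with a Baseline digital inclinometer")
- pain in the same three movements ("Postintervention Numerical Rating Pain Scale in shoulder mobility")
- pressure pain threshold by algometer at two sites.

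That makes 3 + 3 + 2 = 8 post-treatment measurements. None has a responder threshold.

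**The concern.** An effect measure should tell the reader how far apart the arms are, in units that mean something, and how precisely this is known. For degrees of motion, pain points and pressure thresholds, that is a difference in means or in changes with an interval. The SAP names three other quantities. Two of them, relative and absolute risk reduction, need an event. The third is undefined: it could be a sample size worked out from the observed effect, or it could be a rendering of number needed to treat.

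What is at stake is the main quantitative result. If the sentence is followed literally, the report may give p-values and a required sample size but no estimate of the difference. If it is followed in spirit, someone must choose a cut-off for up to eight measurements. Nothing in the plan requires that choice to come before the results are seen, and the size of every risk measure would depend on it.

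**Working it through.** The documents give no N, alpha, power, SD or target difference, so there is no figure in the plan to reproduce. The check takes each reading of the phrase in turn. Two-sided alpha 0.05, 80% power and equal arms are assumptions made here for illustration.

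**Reading 1: a size computed from the observed effect**

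*Two-arm contrast, normal approximation.* The observed statistic is z = d / (SD × √(2/n)). The size per arm needed to detect the observed d is N = 2 × SD² × (1.960 + 0.842)² / d². Substituting d removes both d and SD:

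N / n = (1.960 + 0.842)² / z² = 7.85 / z²

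*Three-arm one-way ANOVA.* The observed F on 2 and 3(n − 1) degrees of freedom is turned into an effect size, f² = 2F / (3n). N is the per-arm size at which the noncentral F test, with noncentrality 3N × f² = 2F × N/n, has 80% power. This was solved numerically for n from 10 to 200 per arm. As a large-sample check, 80% power on 2 degrees of freedom needs a noncentrality of 9.63, and 2F at p=0.05 tends to 5.99, so N / n tends to 9.63 / 5.99 = 1.61.

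| Observed p | z | Two-arm N/n | Three-arm ANOVA N/n |
|---|---|---|---|
| 0.05 | 1.960 | 7.85 / 3.84 = 2.04 | 1.5 to 1.6 |
| 0.20 | 1.282 | 7.85 / 1.64 = 4.78 | 2.9 to 3.0 |
| 0.50 | 0.674 | 7.85 / 0.455 = 17.3 | 6.9 |

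At 90% power the two-arm figure at p=0.05 is (1.960 + 1.282)² / 1.960² = 2.74.

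In the two-arm case the ratio depends on p alone. With n per arm of 10, 20, 50 and 200 and different SDs, the same p gave the same ratio apart from rounding up to whole patients. In the ANOVA it depends on p and, slightly, on n. Once n and the test result are known, the needed size adds nothing about the effect. The ratio is what p fixes; N itself follows once n is known.

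**Reading 2: number needed to treat**

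Number needed to treat = 1 / absolute risk reduction. With illustrative event rates of 50% and 30%, this is 1 / 0.20 = 5, whether n per arm is 20 (p=0.20), 50 (p=0.04) or 200 (p<0.001). It does not restate the p-value, so the objection under reading 1 does not apply.

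It does need two event rates, as do the absolute risk reduction (0.50 − 0.30 = 0.20) and the relative risk reduction (0.20 / 0.50 = 0.40). The Protocol outcomes are an angle, a rating-scale score and a pressure threshold. With no cut-off in either document, none of the three measures can be computed as written.

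**The case against.** The strongest objection is that the phrase is probably a translation slip. Relative risk reduction, absolute risk reduction and a needed number form a familiar set whose third member is number needed to treat. Number needed to treat is an effect measure and a power-based sample size is not, so the stated purpose favours that reading. This stands, and it means the plan cannot simply be said to schedule a post-hoc sample-size calculation. It does not rescue the sentence, because the missing event then defeats all three measures.

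It may also be said that the SAP foresees qualitative variables and a chi-square test, so a responder outcome may be intended. That is possible, but neither document defines one.

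Four stronger inferences are tempting, and the documents do not support them.

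- *That every non-significant result would appear to need at least twice the patients.* The factor of 2.0 belongs to a two-arm contrast at 80% power. For the three-arm ANOVA, which the SAP names, it is 1.5 to 1.6 at p=0.05.
- *That the figure will be used to excuse a null result.* The SAP does not say how a non-significant result will be interpreted.
- *That recruitment may be topped up to the computed size, raising the false-positive rate.* Neither document mentions extension or re-testing. Any error rate would describe a procedure supplied by the reader.
- *That the trial size was never planned.* The words "proceeding a n/2 homogeneity preanalysis" refer to an n without saying how it was chosen, and the front pages were not in the text reviewed. A missing justification is a gap in detail, separate from this point.

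**Conclusion.** The point holds as a mismatch between effect measures and outcomes. All three quantities in the SAP's last sentence are unsuitable as written for the eight measurements in the Protocol. This does not depend on which reading of the needed sample size is correct: one reading gives a restatement of the test result, and the other gives a quantity that cannot be computed from the defined outcomes. The two risk reductions fail for the second reason on either reading.

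The multiples under the first reading rest on assumed values of two-sided 0.05 and 80% power, equal arms, and the observed effect plugged in as if true. The conclusion that the ratio follows from the test result does not rest on those particular values. No numerical size can be put on the second problem, because the documents give no event rates and no cut-off.

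**What to change.** In the SAP's last sentence, delete the needed sample size and the two risk reductions as measures of effect. Replace them with between-arm differences in change from baseline, or differences in baseline-adjusted post-treatment means, each with a 95% confidence interval, for every outcome in the Protocol.

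If a risk-type summary is wanted, name the outcome and fix its responder cut-off in the SAP before any data are seen. Then report the absolute and relative risk reductions and, if intended, number needed to treat under that name, with intervals.

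The cost is a few lines of SAP text, with no additional patients or measurements. The small downside is the loss of a risk-type summary if no cut-off is set in advance.
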